9.9 An Early Withdrawal Visit

Subjects who discontinue early from the study will be asked to complete an early withdrawal visit. The following activities will be performed at the early withdrawal visit:

- Perform physical examination
- Record vital signs
- Collect blood sample for laboratory tests (hematology, chemistry and coagulation) and PK
- Collect urine sample for urinalysis, urine culture, and PK
- Perform urine pregnancy test
- Perform cystoscopy
- Record PRO assessments (BPIC-SS, ICSI/PI, and GRA)

- Collect concomitant medication and therapy information
- Review of subject daily diary
- Record AEs

9.10 Unscheduled Visit

In the event the Investigator needs to conduct follow-up assessments to evaluate an AE, the following safety assessments may be performed on an unscheduled visit:

- Physical examination
- Record vital signs
- Collect blood sample for laboratory tests (hematology and chemistry) and PK if considered appropriate
- Perform cystoscopy, if necessary

10 ADVERSE EVENTS

10.1 Adverse Events

An AE is any untoward medical occurrence that occurs in a subject administered with IP, and that does not necessarily have to have a causal relationship with the treatment. An AE can therefore be any unfavorable and unintended sign (including abnormal laboratory findings and the cystoscopy), symptom, or disease temporally associated with the use of IP, whether or not considered related to the product.

All AEs occurring after obtaining written informed consent will be documented in the subject source record and eCRF. Concomitant illnesses that existed before entry into the study will not be considered AEs unless they worsen after IP administration. All AEs, regardless of the source of identification (eg, laboratory assessments, cystoscopy findings, subject reports) must be documented.

Pre-existing conditions will be recorded in the subject source record and eCRF on the medical history or appropriate page.

TEAE will be defined as an AE that begins or that worsens in severity after IP has been administered.

All AEs will be coded using Medical Dictionary for Regulatory Activities (MedDRA) terminology.

AE will be reported by the subject (or, when appropriate, by a caregiver, surrogate, or the subject's legally authorized representative).

The Investigator and any designees are responsible for detecting, documenting, and recording events that meet the definition of an AE or SAE and remain responsible for following up AEs that are serious, considered related to the study treatment or study procedures, or that caused the subject to discontinue the study treatment (see [Section 5.1](#) and [5.2](#)).

10.2 Serious Adverse Events

An SAE is defined as any untoward medical occurrence at any dose that:

- Results in death
- Is life-threatening, meaning that the subject is at risk of death at the time of the event; it does not mean that the event hypothetically might have caused death if it were more severe
- Requires inpatient hospitalization or prolongation of existing hospitalization
- Results in persistent or significant disability/incapacity
- Results in a congenital anomaly/birth defect
- Is an important medical event(s) that may not be immediately life-threatening or result in death or hospitalization but that may jeopardize the subject or require intervention to prevent one of the above outcomes. Examples of such events are invasive or malignant cancers, intensive treatment in an emergency room or at home for allergic bronchospasm; blood dyscrasias or convulsions that do not result in hospitalization or development of drug dependency or drug abuse

Medical and scientific judgment should be exercised in deciding whether a case is serious and whether expedited reporting is appropriate.

AEs reported from clinical studies and associated with hospitalization or prolonged hospitalization are considered serious. Any hospitalization except observational admissions of less than 24 hours for logistical reasons meets these criteria. This category also includes transfer within the hospital to an acute/intensive care unit (eg, from a standard-of-care unit to an acute/intensive care unit).

Hospitalization does not include the following:

- Rehabilitation facilities, hospice facilities, or respite care (eg, caregiver relief)
- Nursing homes or skilled nursing facilities
- Emergency room visits
- Same-day surgeries (such as outpatient/same day/ambulatory procedures)
- <24-hour admissions for observation or evaluation for logistical reasons

Hospitalization or prolongation of hospitalization in the absence of a precipitating, clinical AE is not in itself an SAE. Examples include the following:

- Admission for treatment of a pre-existing condition that did not worsen
- Hospitalizations for cosmetic elective surgery, social, and/or convenience admissions
- Pre-planned treatments or surgical procedures, which should be noted in the baseline documentation for the individual subject

10.3 Cystoscopy, Vital Signs, Electrocardiograms and Laboratory Tests

If an abnormal findings of cystoscopy, vital signs, ECGs or laboratory tests are observed, the Investigator should judge whether it is an AE or not by referring to the following criteria:

- When any medical intervention such as pharmacotherapy or surgical care is performed in order to improve the abnormality
- Other than case above, when investigator judges that the abnormality is medically important and should be considered an AE

10.4 Process for Collecting Adverse Events and Serious Adverse Events Information

All AEs and SAEs will be collected from the signing of the ICF continuously until Day 29 as specified in the Schedule of Activities (See [Table 1](#)).

Medical occurrences that begin before the start of study treatment but after obtaining informed consent will be recorded on the medical history/current medical conditions section in the eCRF not the AE section.

All SAEs during study treatment period will be recorded and reported to the Sponsor or designee within 24 hours, as indicated in [Appendix 12](#).

The Investigator will submit any updated SAE data to the Sponsor or designee within 24 hours of it being available.

Investigator will conduct physical examination to collect on Screening, Day 1 (pre-dose), Day 2, Day 3, Day 5, Day 8, Day 15 and Day 29 or an early withdrawal visit. Investigators should pay special attention to clinical signs related to previous serious illnesses.

Investigators are not obligated to actively seek AE or SAE reports from former study subjects. However, if the Investigator learns of any SAE, including a death, at any time after a subject has been discharged from the study, and he/she considers the event to be reasonably related to the study treatment or study participation, the Investigator must promptly notify the Sponsor.

The method of recording, evaluating, and assessing causality of AE and SAE and the procedures for completing and transmitting SAE reports are provided in [Appendix 12](#).

10.5 Method of Detecting Adverse Events and Serious Adverse Events

Care will be taken not to introduce bias when detecting AEs and/or SAEs. Open-ended and non-leading verbal questioning of the subject is the preferred method to inquire about AE occurrences.

10.6 Follow-up of Adverse Events and Serious Adverse Events

After the initial AE/SAE report, the Investigator is required to proactively follow each subject at subsequent visits/contacts. All SAEs will be followed until resolution, stabilization, the event is otherwise explained, or the subject is lost to follow-up (as defined in [Section 5.3](#)). Further information on follow-up procedures is given in [Appendix 12](#).

10.7 Regulatory Reporting Requirements for Serious Adverse Events

Prompt notification (within 24 hours) by the Investigator to the Sponsor of a SAE is essential so that legal obligations and ethical responsibilities towards the safety of subjects and the safety of a study treatment under clinical investigation are met.

The Sponsor has a legal responsibility to notify both the local regulatory authority and other regulatory agencies about the safety of a study treatment under clinical investigation. The Sponsor will comply with country-specific regulatory requirements relating to safety reporting to the regulatory authority, IRB, and Investigators.

Investigator safety reports must be prepared for suspected unexpected serious adverse reactions according to local regulatory requirements and Sponsor policy and forwarded to Investigators as necessary.

An Investigator who receives an Investigator safety report describing a SAE or other specific safety information (eg, summary or listing of SAEs) from the Sponsor will review and then file it along with the Investigator's Brochure and will notify the IRB, if appropriate according to local requirements.

10.8 Pregnancy

Details of all pregnancies in female subjects and, if indicated, female partners of male subjects which occur during the study, will be collected.

If a pregnancy is reported, the Investigator should inform the Sponsor within 24 hours of learning of the pregnancy.

Abnormal pregnancy outcomes (eg, spontaneous abortion, fetal death, stillbirth, congenital anomalies, ectopic pregnancy) are considered SAEs.

11 STATISTICAL METHODS

While key analyses are described in this section, additional analyses, including supportive analysis, sensitivity analysis, and subgroup analysis, and details such as data handling will be specified in the statistical analysis plan (SAP).

The impact of COVID-19 will be evaluated i.e. based on the missing data, and if deemed necessary appropriate sensitivity analyses will be performed and documented.

11.1 Analysis Populations

11.1.1 Intention-to-treat Population

The intention-to-treat (ITT) population includes all randomized subjects regardless of whether the subject received any IP or had any efficacy assessment collected.

11.1.2 Per Protocol Population

The Per-protocol (PP) population includes all ITT subjects without major protocol deviation.

11.1.3 Safety Population

The safety population includes all randomized subjects who received IP. If a subject receives IP other than the subject's randomized treatment assignment, then the subject is assigned to the treatment arm reflecting the treatment that the subject actually received during the study.

11.1.4 Pharmacokinetic Population

The PK population includes all subjects who received SI-722 and who provided at least 1 evaluable PK sample.

11.2 Demographics, Baseline Characteristics, Medical History, and Concomitant Medications

Subjects' age, height, weight, and other continuous baseline characteristics will be summarized using descriptive statistics, while sex, race, and other categorical variables will be provided using frequency tabulations. Medical history and concomitant medications will be summarized using frequency tabulations by system organ class and preferred term of the MedDRA and Anatomical Therapeutic Chemical class and standardized drug name of WHO Drug Global, respectively.

11.3 Pharmacokinetic Analyses

Plasma and urine concentrations of SI-722 and [REDACTED] will be determined for the safety population. The other PK analyses will be determined based on the PK population.

Pharmacokinetic profiles will be assessed by plasma SI-722 and [REDACTED] concentrations, urine SI-722 and [REDACTED] concentrations, and the corresponding PK parameters.

The following PK parameters for SI-722 and [REDACTED] will be estimated, where possible, using Phoenix WinNonlin v8.0 software (or higher) and actual blood sample collection times:

Plasma PK parameter

C_{\max} maximum concentration after dosing

t_{max}	time to reach the maximum plasma concentration
AUC_{0-t}	area under the plasma concentration-time curve from time 0 to t hours after dosing, in which time t is the last time at which the concentration can be observed in all cohorts.
AUC_{0-last}	area under the concentration-time curve from time 0 to time the last quantifiable concentration
$AUC_{0-\infty}$	area under the plasma concentration-time curve from time 0 to infinite time, calculated as the sum of AUC_{last} and C_{last}/λ_z , in which C_{last} is the last observed quantifiable concentrations
$t_{1/2}$	terminal half-life
V_z/F	apparent volume of distribution
CL/F	apparent total plasma clearance

Urine PK parameter

A_e	cumulative amount of excreted in urine
-------	--

Details will be outlined in the SAP. Additional PK parameters will be estimated and analyzed if needed.

11.4 Safety Analyses

All safety analyses will be conducted based on the safety population.

11.4.1 Adverse Events

AEs will be analyzed in terms of TEAEs, defined to be any event that begins or worsens in grade after the start of IP throughout of the study. All AEs will be coded using MedDRA.

The number of events and number (percentage) of subjects reporting TEAEs for each preferred term will be tabulated by system-organ class, by system-organ class and severity, and by system-organ class and relationship to IP. If more than 1 event occurred with the same preferred term for the same patient, the subject will be counted only once for that referred term using the most severe or related occurrence for the summary by severity, or relationship to IP, respectively.

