1.3 Summary of Possible Risk and Benefits to Subjects

1.3.1 Possible Risks

Safety data obtained from nonclinical and clinical studies indicated that there were no major safety concerns and SI-722 has an acceptable safety profile.

Based on the results of Phase 1 study, dysuria, hematuria, and urethral irritation were identified as potential risks. No severe or serious events related to the urinary system were reported, but as a precaution, any changes of urinary function will be carefully monitored in the phase 1/2 clinical study.

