8.2.2 Cystoscopy

- Assessment Points: Cystoscopy will be performed on Day 1 (pre-dose) to identify presence or absence of Hunner's lesion as well as Day 8, and Day 29 or an early withdrawal visit to evaluate abnormal change from Day 1.
- Method: Subjects must fully void their bladders after the cystoscopy procedure in preparation for the IP instillation. About five photographs inside the bladder will be printed and filed with each subject's source document.

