An event is defined as 'serious' when it meets at least 1 of the predefined outcomes as described in the definition of an SAE, NOT when it is rated as severe.

Assessment of Causality

- The Investigator is obligated to assess the relationship between study treatment and each occurrence of each AE/SAE.
- A "reasonable possibility" of a relationship conveys that there are facts, evidence, and/or arguments to suggest a causal relationship, rather than a relationship cannot be ruled out.
- The Investigator will use clinical judgment to determine the relationship, either as not related or related.

Not Related: There is not a reasonable possibility that the administration of the study intervention caused the event, there is no temporal relationship between the study intervention and event onset, or an alternate etiology has been established.

Related: The AE is known to occur with the study intervention, there is a reasonable possibility that the study intervention caused the AE, or there is a temporal relationship between the study intervention and event. Reasonable possibility means that there is evidence to suggest a causal relationship between the study intervention and the AE.

Alternative causes, such as underlying disease(s), concomitant therapy, and other risk factors, as well as the temporal relationship of the event to study treatment administration will be considered and investigated.

- The Investigator will also consult the Investigator's Brochure (IB) and/or Product Information, for marketed products, in his/her assessment.
- For each AE/SAE, the Investigator **must** document in the medical notes that he/she has reviewed the AE/SAE and has provided an assessment of causality.
- There may be situations in which an SAE has occurred and the Investigator has minimal information to include in the initial report to the medical monitor or Sponsor. However, **it is very important that the Investigator always make an assessment of causality for every event before the initial transmission of the SAE data to the medical monitor or Sponsor.**
- The Investigator may change his/her opinion of causality in light of follow-up information and send a SAE follow-up report with the updated causality assessment.
- The causality assessment is one of the criteria used when determining regulatory reporting requirements.

Follow-up of AEs and SAEs

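### Causality is judged only against study treatment, under overlapping definitions, so urinary events caused by cystoscopy or catheterisation can be counted as IP-related

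*Combined protocol and SAP*

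**What the plan says.** Section 11.4.1 counts as treatment-emergent anything "defined to be any event that begins or worsens in grade after the start of IP throughout of the study", whatever its cause. It tabulates these events "by system-organ class, by system-organ class and severity, and by system-organ class and relationship to IP". Within a preferred term each subject counts once, and a related occurrence takes precedence in the relationship table.

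The causality part of Appendix 12 states: "The Investigator is obligated to assess the relationship between study treatment and each occurrence of each AE/SAE". It allows two answers: "The Investigator will use clinical judgment to determine the relationship, either as not related or related". One sufficient ground for related is given as "or there is a temporal relationship between the study intervention and event". One sufficient ground for not related is that another cause has been established.

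On procedures, Section 8.2.2 says: "Cystoscopy will be performed on Day 1 (pre-dose) to identify presence or absence of Hunner's lesion as well as Day 8". A further cystoscopy follows on Day 29 or at early withdrawal. Section 7.2 gives the product through a bladder catheter. Section 1.3.1 reports from Phase 1 that "dysuria, hematuria, and urethral irritation were identified as potential risks".

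Section 10.1 makes investigators responsible for following up events "considered related to the study treatment or study procedures", so the protocol expects some events to be procedure-related. No causality item or table that it describes records that judgement.

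**The concern.** The urinary events named as product risks are of the kind that passing a cystoscope or catheter could also produce. On Day 1 cystoscopy, catheterisation and instillation follow one another, so timing alone cannot separate their effects. If the only causality question concerns study treatment, and timing alone is enough to answer it with related, the IP-related table can absorb procedure effects to a degree that depends on how each investigator reads Appendix 12.

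Safety and tolerability is a primary objective. Section 6.8 directs the Safety Review Committee's attention to urologic events before each dose step, when the current cohort offers only 2 placebo subjects as a reference. Attribution not recorded at the time is hard to recover later.

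**Working it through.** **Plan's own figure.** Sections 3.2 and 3.4 give four cohorts randomised 6:2. That is 4 × 6 = 24 SI-722 and 4 × 2 = 8 placebo, total 32, as stated.

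**Definitions side by side.** Take dysuria that begins an hour after instillation, with catheter trauma documented.
- Treatment-emergent (11.4.1): yes, because onset is after the start of IP.
- Related (Appendix 12): met, because it is close in time to the study intervention.
- Not related (Appendix 12): also met, because another cause is established.
- Procedure-related (10.1): recognised as a reason for follow-up, with no described field or table.

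Two investigators can code the same event oppositely and both comply. If dysuria recurs after the Day 8 cystoscopy, the once-per-term rule merges the episodes, and a related call on either one sets the subject's entry.

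**Assumption.** The documents give no rate of procedure-caused urinary events. Let q be the chance that a subject has one starting after instillation, independent between subjects, with no drug effect. I use q = 0.2 and 0.4, and a wider range below.

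**Scope for misattribution.** Expected SI-722 subjects with such an event: 24q = 4.8 at q = 0.2 and 9.6 at q = 0.4. For placebo: 8q = 1.6 and 3.2. The number entered as IP-related could lie anywhere from none to all of these, depending on which definition is followed.

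**One cohort at review.**
- At least 1 event in 6 SI-722 subjects, 1 − (1 − q)^6: 0.738; 0.953.
- No event in 2 placebo subjects, (1 − q)^2: 0.640; 0.360.
- Both together: 0.738 × 0.640 = 0.472; 0.953 × 0.360 = 0.343.
- In at least one of four cohorts: 1 − (1 − 0.472)^4 = 0.92; 1 − (1 − 0.343)^4 = 0.81.

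At q = 0.1, 0.3 and 0.5 the per-cohort probability is 0.38, 0.43 and 0.25. With at least 2 of 6 against 0 of 2, it is 0.09, 0.22, 0.28 and 0.22 at q = 0.1, 0.2, 0.3 and 0.5.

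**What placebo can show.** Zero events in 2 subjects has an exact 95% upper limit of 1 − 0.025^(1/2) = 84%. Zero in the pooled 8 gives 1 − 0.025^(1/8) = 37%. The chance that the pooled 8 show at least one event, 1 − (1 − q)^8, is 0.83 at q = 0.2 and 0.98 at q = 0.4.

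**The case against.** The strongest reply is that placebo already controls for procedures. Placebo subjects have the same cystoscopies and catheterisation, investigators and subjects are blinded (Section 6.6), and Section 11.6 pools all 8 placebo subjects. This stands for the all-cause comparison. A reader might infer that the comparison of SI-722 with placebo is biased; the documents do not support that. Blinding also means that placebo's related counts are inflated by the same mechanism, so the distortion concerns related counts read on their own. Placebo data also accumulate to 2, 4 and 6 subjects by the three escalation decisions, and nothing bars the committee from using earlier cohorts. However, Section 6.8 describes its interim report as prepared for the cohort under review.

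A reader might also infer that procedure-caused events must be called IP-related. They need not be, since an established alternative cause permits not related and Appendix 12 requires alternative causes to be considered. But not related does not identify the procedure as the cause, and the temporal ground remains open for the same event.

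Counting these events as treatment-emergent is not an error. The definition rests on onset, and catheter effects belong to the tolerability of an instilled product. Nor are events after the Day 8 cystoscopy impossible to interpret: onset dates, placebo and serial urinalysis all help. The committee's minimum data also stop at Day 8, so many of these events need not enter the escalation decision.

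Finally, the 6-versus-2 contrast follows from the allocation and would remain after the fix, and no stated rule makes one event in six decisive. That is right: the figure shows how little 2 placebo subjects tell the committee about procedure background, which is why recorded attribution would help. Section 11 defers further analyses to a SAP, and neither separate SAP text nor the eCRF pages are in the public documents, so a field may exist there. The causality assessment as written would not require it.

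**Conclusion.** The point holds for the related counts and for cohort-level review. It does not extend to the pooled all-cause comparison with placebo, which the design protects in expectation. The overlap between the two causality definitions is a matter of text and needs no assumption. Its numerical effect does. With an assumed procedure-event rate of 20% to 40% and no drug effect, 4.8 to 9.6 of 24 SI-722 subjects would be expected to have an event whose attribution depends on the reading of Appendix 12. A cohort would show events on SI-722 alone with probability 47% at the 20% rate and 34% at the 40% rate. These figures illustrate the uncertainty and do not estimate a bias. The point is limited to events that begin or worsen after instillation, because earlier ones are not treatment-emergent. It is worth correcting because safety is a primary objective and the remedy is small.

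**What to change.** - In Appendix 12 and on the adverse-event eCRF page, add a separate yes/no item: related to study procedure (cystoscopy or catheterisation). Keep it independent of relationship to IP, so that both can be answered yes.
- Reconcile the related and not-related definitions so that one event cannot satisfy both, and align them with Section 10.1's reference to study procedures.
- In Section 11.4.1 and the Safety Review Committee report, keep all urinary treatment-emergent events by treatment group, regardless of cause, as the main table.
- Add a supportive table by both relationships and by onset period: Day 1 to before the Day 8 cystoscopy; from that cystoscopy to before the Day 29 cystoscopy; and after the Day 29 cystoscopy. Define the periods by the actual procedure date and time, since Sections 9.6 and 9.8 allow ±3 and ±5 days. The last period will be short because event collection ends at Day 29. In committee reports, show placebo for the current cohort and cumulatively.

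The cost is one eCRF field, one clarified definition and one extra table. The downside is that procedure attribution is a subjective, blinded judgement. It cannot reliably separate drug from catheter effects on Day 1, and it may move genuine drug effects out of the IP-related count. It must therefore remain supportive and must not remove any event from the main table.
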